9.6. Exploratory Analyses

 Composite endpoint of hospitalization, oxygen desaturation, oxygen requirement, mechanical ventilation, or death by 28 days after study entry. Hospitalization is defined as ≥24 hours of acute care. Oxygen desaturation is defined as oxygen saturation ≤93%, measured using pulse oximetry. Oxygen requirement will be measured using the World Health Organization (WHO) ordinal scale

The number and percent of subjects meeting the endpoint criteria during the 28 days will be summarized by treatment.

• Comparability between viral RNA non-negativity (i.e., above the limit of quantification) and virus isolation non-negativity from site collected NP swabs

The viral RNA qualitative results (below or above the limit of quantification) determined by RT-PCR and the qualitative results determined (Positive or Negative) by infectious virus detection cell cultures will be presented in a cross tabulation table. Cohen's kappa statistic will be estimated for the assessment of the between assay agreement.

10. CLINICAL PHARMACOLOGY DATA ANALYSES

10.1. Pharmacokinetic Analyses

Sparse blood sampling will be collected on Day 5, at prior to the morning dose, and where possible at approximately 1 and 2 hours after the morning dose. Plasma EIDD-2801/EIDD-1931 concentrations will be determined by validated analytical procedures.

Plasma concentration data will be summarized descriptively by planned time point.

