6.2.16. Pharmacokinetics

Per the SOE, sparse PK sampling will be collected at sites that are able to obtain and process PK samples. Day 5 blood collection may be used to measure drug levels to assess the relationship between drug exposure and viral elimination dynamics including time to clearance.

When possible, participants should fast overnight before their Day 5 visit (i.e., participants should arrive at the Day 5 visit having had no food or drink intake except for water in the previous 8 hours).

Specifically, blood will be collected for sparse PK measurements at the following timepoints, where possible:

- Just prior to the morning dose on Day 5 (trough)
- Approximately 1-hour post morning dose on Day 5
- Approximately 2-hours post morning dose on Day 5 (if possible)

The timing of the post-dose samples may be adjusted for individual participants to increase the range of timepoints for PK evaluation. No participant will have more than 3 PK samples taken. The approximate time of the 3 doses preceding the PK sampling, the exact time of the dose

immediately preceding the PK sample, the time of the most recent meal, and the exact time of each PK sample collection should be recorded.

If it is determined that sufficient PK samples have been collected to characterize the PK profile in this patient population, PK sample collection may be discontinued by the Sponsor at any time.

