10.7.2. Pharmacokinetic and Pharmacokinetic-Pharmacodynamic Analyses

Plasma concentrations of EIDD-2801 and EIDD-1931 will be listed and summarized by treatment and scheduled time point. A PK-pharmacodynamic (PD) model will also be developed to examine the relationship between EIDD-2801/EIDD-1931 PK, viral load reduction, and clinical outcomes. Details of PK and PK-PD analyses will be provided in the SAP.

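### SAP 10.1 summarises plasma concentrations by planned time, but the protocol allows post-dose sampling times to be varied, so the 1 h and 2 h rows may mix different real times

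*SAP*

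**What the plan says.** Protocol 6.2.16 schedules up to three sparse samples on Day 5: a trough before the morning dose, then one at about 1 h and one at about 2 h after it. It adds: "The timing of the post-dose samples may be adjusted for individual participants to increase the range of timepoints for PK evaluation". It gives no bound on that adjustment. It asks for the exact time of the dose immediately before the sample, and says that "the exact time of each PK sample collection should be recorded".

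SAP 10.1 repeats the nominal scheme, a pre-dose sample and then, "where possible at approximately 1 and 2 hours after the morning dose", the two post-dose samples. Its analysis rule is one sentence: "Plasma concentration data will be summarized descriptively by planned time point". It does not mention the permitted adjustment, and it gives no acceptance window, time-after-dose category or display on actual time. SAP 10.2 relates the Day 5 pre-dose trough to the Day 5 change in viral RNA and makes no specified use of the post-dose values.

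The protocol's own statistics section, 10.7.2, has a similar rule: "Plasma concentrations of EIDD-2801 and EIDD-1931 will be listed and summarized by treatment and scheduled time point". It goes on to say that "A PK-pharmacodynamic (PD) model will also be developed" and that "Details of PK and PK-PD analyses will be provided in the SAP". SAP section 11, which lists changes from the protocol, says nothing about PK.

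**The concern.** Spreading sampling times between participants is a sensible device in a sparse design, but it pays off only if the analysis uses the time at which each sample was drawn. A table keyed to the planned time does not use it. A sample moved from 2 h to, say, 4 h would still be averaged in the 2 h row. Its low value would then read as a low 2 h concentration, and the differences in timing would appear in the row's standard deviation as if they were differences between people.

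Characterising PK in patients is a secondary objective in both documents. Because several doses are studied, readers will naturally compare rows across dose groups. If the shifts were more frequent or larger in one group than in another, part of an apparent dose difference would be a timing difference.

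**Working it through.** The plan states no figure on this point: no PK sample size, precision target, half-life, time of peak or window. There is nothing to reproduce, so the check is a comparison of texts followed by an illustration on assumed values.

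**Which samples are exposed**

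| Sample | May its time be shifted? (protocol 6.2.16) | Specified use in the SAP | Can rows mix real times? |
|---|---|---|---|
| Pre-dose | No, the permission covers post-dose samples only | Row in the 10.1 table; 10.2 regression | No |
| About 1 h | Yes | Row in the 10.1 table | Yes, where the permission is used |
| About 2 h | Yes | Row in the 10.1 table | Yes, where the permission is used |

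The cap is three samples per participant, so at most two of the three are exposed. SAP section 5 keeps the last of several assessments at one scheduled time, but it has no rule for moving a PK sample to another time label.

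**Illustration of size.** Every input here is an assumption and none comes from the documents: a one-compartment oral model, a half-life h of 1, 2 or 4 h, an absorption rate ka of 1.5 or 3 per hour, and the size of the shift.

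C(t) ∝ exp(−ke·t) − exp(−ka·t), with ke = ln 2 / h.

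The two extremes for a sample labelled 2 h but drawn at 4 h are:

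- h = 4, ka = 1.5, so ke = 0.173. C(2) ∝ 0.707 − 0.050 = 0.657 and C(4) ∝ 0.500 − 0.002 = 0.498. The ratio is 0.76, or 24% low.
- h = 1, ka = 3, so ke = 0.693. C(2) ∝ 0.2500 − 0.0025 = 0.2475 and C(4) ∝ 0.0625 − 0.0000 = 0.0625. The ratio is 0.25, or 75% low.

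Over all six combinations of h and ka:

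| Real draw time for a sample labelled 2 h | Value relative to the true 2 h concentration |
|---|---|
| 3 h | 0.50 to 0.89 |
| 4 h | 0.25 to 0.76 |
| 6 h | 0.06 to 0.54 |

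If a 2 h row held equal numbers of samples drawn at 2, 4 and 6 h, its mean would be 0.44 to 0.76 of the true 2 h value. For example, with h = 1 and ka = 3, (1 + 0.25 + 0.06)/3 = 0.44. Timing alone would give that row a coefficient of variation of about 25% to 92%.

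For the 1 h row not even the direction can be stated. Under the same assumptions a draw at 0.5 h gives 0.72 to 1.07 of the 1 h value, and a draw at 1.5 h gives 0.76 to 1.08, because 1 h may lie on either side of the peak.

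**The case against.** The strongest reply is that this is a small descriptive table and that the SAP does what the protocol's statistics section asked for. That is correct on both counts. Protocol 10.7.2 also summarises by scheduled time, so the tension lies inside the protocol, between its sampling section and its statistics section, and the SAP inherits it. A reader might infer that the SAP departs from the protocol's planned summary on this point. On the choice of time axis it does not.

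The permission is also only that. Times may be adjusted, and nothing shows how often, by how much, or whether this was done. If few samples move, the nominal table is close to right.

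It could be argued that planned time means each participant's re-planned time, in which case rows would not mix. The SAP does not say so, and the only times it names are pre-dose, 1 h and 2 h.

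Two stronger readings are tempting and should be resisted:

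- **That SAP 10.1 pools doses because it omits a treatment split.** Protocol 10.7.2 asks for the summary by treatment, protocol 10.7 makes summaries by treatment group the general method, SAP section 6.1 defines display groups by dose, and SAP section 11 declares no PK change. A missing phrase in one sentence does not show a plan to average across doses.
- **That shifted post-dose samples have no use outside this table.** The protocol commits to listings and to a PK-PD model, SAP 10.2 leaves room for further models if the data warrant, and SAP 5.2 sets summary statistics for PK parameters. It is fair to say that the SAP specifies no model that uses these samples, but not that none could.

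What stands is the core: sampling times may be varied on purpose, and the only analysis specified for the varied samples ignores the times.

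**Conclusion.** The point holds, within limits. Where the protocol's permission is used, the 1 h and 2 h rows of the SAP 10.1 table may combine samples drawn at different real times. Their means may then be biased and their spread inflated. The pre-dose row and the SAP 10.2 trough regression are untouched, and no efficacy or safety test depends on the table. What is at stake is how well a secondary objective is described.

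The figure of about 24% to 75% low for a 2 h sample drawn at 4 h rests wholly on an assumed half-life of 1 to 4 h, assumed first-order absorption and an assumed two-hour shift. It shows that the effect need not be trivial. It does not estimate what will happen in this trial.

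**What to change.** In SAP 10.1, list, plot and summarise post-dose concentrations by dose group and actual time after dose, in windows fixed in advance. Examples are 0.5–1.5 h, 1.5–2.5 h and later, with the shared boundary assigned to one window and a stated place for any sample drawn before 0.5 h. State which sample counts if two from one participant fall in the same window. Keep the pre-dose row as it is. Naming the dose group in the sentence also closes off the pooling misreading. Add that any exposure or PK-PD model that is fitted will use the recorded dose and sample times.

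The cost is a short SAP revision before database lock and minor programming. No new data are needed, because protocol 6.2.16 already has the exact times recorded. The trade-off is fewer samples per row once they are spread over more windows. A population PK model on the recorded times would be a reasonable option, but it means real extra work and correcting the table does not require it.

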10.2. Pharmacokinetic and Pharmacodynamic Analyses

The response-response relationship between Plasma EIDD-2801/EIDD-1931 trough concentration (pre-dose at day 5) and efficacy endpoint (i.e., change from baseline in SARS-CoV-2 RNA at day 5) will be analyzed using a simple linear model. The paired concentration and efficacy endpoint(s) will be plotted with a fitted regression line superimposed. Additional statistical models will be explored if the data warrant.

11. CHANGE FROM ANALYSIS PLANNED IN PROTOCOL

Due to lack of availability of subjects in the "early" time from symptom onset stratum, the between group comparison for the time to non-detectable SARS-CoV-2 viral RNA will be performed using an un-stratified log-rank test.

Statistical comparisons of safety endpoints between treatment groups in Part 1 will not be performed. All safety data will be presented descriptively.

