10.5. Sample Size and Accrual

The proposed total sample size for the study is up to approximately 172 fully evaluable participants. If participants in a dose group drop out or otherwise have missing or unevaluable primary or key secondary virology endpoint data, additional participants may be enrolled to ensure adequate data at each dose level. The total number of participants to be enrolled will not exceed 204.

For Part 1 of the study, the planned sample size is approximately 44 participants who take the first (confirmed) dose of study treatment (approximately 22 each in Arms A and B).

In subsequent, optional study parts, the sample size **for each part** will include approximately 16 participants who take the first (confirmed) dose of study treatment (approximately 12 participants randomized to an active EIDD-2801 arm and 4 randomized to placebo). Participants who are randomized but do not take the first (confirmed) dose of study treatment will not be followed and will be replaced.

This study is designed to evaluate the antiviral activity of EIDD-2801 by estimating the time (days) until elimination of viral RNA detection in NP swabs in people who receive EIDD-2801 compared to those who receive a blinded placebo. Kaplan-Meier estimation will be used with a corresponding exact, stratified log-rank test (for Part 1) and median time (days) until first non-detectable SARS-Cov-2 NP swabs will be estimated in each trial arm.

Power/Sample Size for Part 1:

The distribution of days until SARS-CoV-2 viral RNA is not detectable (i.e., below the limit of quantification in NP swabs) can be compared between the 2 trial arms (drug vs placebo) using an exact log-rank test. At a 0.10 type I error probability and under the assumptions in Figure 8 and the corresponding table below, there is >85% power to detect a difference (Drug - Placebo) of at least 30% if the evaluable sample size is 19 individuals per arm.

Anticipating up to 10% missing data, enrolling n=44 participants total (approximately 22 per arm) in Part 1 will provide 88% power for the primary endpoint. Power was calculated empirically in R version 3.6.2 using 5000 simulated datasets.

- The power to detect a risk difference (RD) (Drug Placebo) of -30% is 0.88.
- The power to detect a RD (Drug Placebo) of -40% is 0.98.
- The power to detect a RD (Drug Placebo) of -50% is >0.99

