10.7.3.1. Primary Outcome Measures

Virologic Efficacy: The distribution of days until first non-detectable SARS-CoV-2 viral RNA in NP swabs will be estimated for each randomized arm (drug versus placebo), using Kaplan-Meier methods with a corresponding exact stratified log-rank test (Part 1 only: to account for the "early" versus "late" time from symptom onset randomization strata). "Non detectable" will be defined as a viral load below the limit of quantification (BLOQ). Two consecutive non-detectable viral RNAs in NP swabs (or one negative with no further follow-up) will be required to achieve the event. The date of the first non-detectable will be the event date. Participants who prematurely discontinue the study before achieving non-detectable results will have follow-up for efficacy endpoints censored at the date of last measurement. Losses to follow-up will be assumed non-informative.

Safety and Tolerability: In order to measure the safety and tolerability of EIDD-2801, we will estimate by randomization arm the probability of 1) any AEs leading to early discontinuation of blinded treatment (active or placebo), 2) study drug-related discontinuation of treatment, 3) new grade 3 or higher AE (not already present at baseline), and 4) study drug-related new grade 3 or higher AE. The cumulative probability (i.e., risk) of each safety and each tolerability endpoint (4 endpoints) will be estimated using the Kaplan-Meier approach and stratified log-rank test will be employed for between trial arm comparisons (as outlined for the primary efficacy outcome). Follow-up will be right censored at the date of last known status and event times will be the date of first onset of the given endpoint (e.g., time to first AE leading to early discontinuation of blinded treatment).

The safety and tolerability profile of EIDD-2801 in humans is currently not fully characterized and descriptive participant-level listings of safety and tolerability events will be summarized. We will estimate 28-day risk function of each safety and tolerability endpoint with a corresponding 2-sided 90% confidence interval, with focus on the upper confidence limit for interpretation of results. To inform the design of future larger trials we will estimate the difference in probabilities

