3.3. Randomization

In Part 1 of the study, eligible participants will be randomized using a 1:1 ratio to Arm A or B using permuted blocks. In all subsequent study parts, eligible participants will be randomized using a 3:1 ratio (EIDD-2801:placebo) to Arm C or D (Part 2), Arm E or F (Part 3), Arm G or H (Part 4), Arm I or J (Part 5), Arm K or L (Part 6), Arm M or N (Part 7), Arm O or P (Part 8), or Arm Q or R (Part 9).

In Part 1, randomization will be stratified by "early" versus "late" time from symptom onset, where "early" time from symptom onset is defined by enrollment (i.e., randomization date and time) 0 to ≤ 60 hours from symptom onset and "late" is enrollment (i.e., randomization date and time) > 60 to ≤ 168 hours from symptom onset. In subsequent study parts, randomization will not be stratified due to lack of availability of subjects in the "early" time from symptom onset.

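### Part 1 is randomized within onset strata, but the SAP drops them from the primary log-rank test without giving the early-stratum count; the effect ranges from nil to a conservative test that loses about 2 to 4 points of power

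*SAP*

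**What the plan says.** **Randomization.** For Part 1, SAP section 3.3 says that "eligible participants will be randomized using a 1:1 ratio to Arm A or B using permuted blocks", with stratification by early (0 to 60 hours) or late (over 60 to 168 hours) onset. Protocol sections 3 and 10.4 say the same. For the later parts the strata are dropped: "In subsequent study parts, randomization will not be stratified due to lack of availability of subjects" in the early group.

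**Protocol test.** Section 10.7.3.1 plans the primary comparison "using Kaplan-Meier methods with a corresponding exact stratified log-rank test", and limits the stratification to Part 1 to reflect the randomization strata. The design paragraph of section 10.5 also calls the Part 1 test stratified. The power paragraph of the same section does not: the distributions "can be compared between the 2 trial arms (drug vs placebo) using an exact log-rank test".

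**SAP test.** Sections 2.3 and 3.2.1 name an exact log-rank test with no strata. Section 11 lists the change from the protocol and opens with the reason, "Due to lack of availability of subjects in the" early stratum, and then says that "the between group comparison for the time to non-detectable SARS-CoV-2 viral RNA will be performed using an un-stratified log-rank test".

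**Not stated in either document.** The number of early participants, a threshold below which the strata would be dropped, and any stratified sensitivity analysis.

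**The concern.** Under SAP section 2.3, this Part 1 comparison is the only hypothesis formally tested. None is tested in Parts 2 to 9 or for safety.

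Permuted blocks within strata hold the arms close to balance on onset time. If onset time predicts clearance, that balance makes the between-arm difference less variable than the un-stratified variance formula assumes. The test then rejects less often than its nominal 10% under the null and gives up power under the alternative.

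The stated reason does not settle the matter. The protocol already recorded the shortage of early presenters when it dropped strata for the later parts (section 10.4), yet it kept the stratified test for Part 1. A small stratum adds little to a stratified log-rank statistic but does not make it invalid.

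Nor does the SAP adjust for onset time elsewhere. Protocol section 10.8 planned days since infection as an ANCOVA covariate, but the MMRM and ANCOVA models in SAP section 9.1 have no such term. SAP section 5.3.6 only allows that baseline characteristics may be explored as covariates.

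**Working it through.** **Inputs from the documents.** 19 evaluable per arm, 38 in all (protocol 10.5). Two-sided alpha of 0.10 (protocol 10.7.3). Post-baseline swabs on Days 3, 5, 7, 14 and 28. Placebo detection on those days of 88, 71, 52, 10 and 0% (table under Figure 8). The active curve is the placebo curve minus the risk difference (RD), floored at zero. For RD -30% that is 58, 41, 22, 0 and 0%.

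**Assumptions, because the documents give no figures.** Block size 4. An early stratum of 0 to 19 of the 38. Early-stratum detection shifted on the logit scale: logit S_early(t) = logit S(t) + shift, with shift 0, 0.5, 1 or 2. To give a sense of scale, placebo Day 7 detection of 52% has logit ln(0.52/0.48) = 0.08. A shift of 1 makes it 1/(1+e^-1.08) = 75%, and a shift of 2 makes it 1/(1+e^-2.08) = 89%. A shift of 2 is therefore strong.

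**Tests.** At each visit, O − E = d1 − d·n1/n with hypergeometric variance V, where d and n are events and numbers at risk and subscript 1 is the active arm. The un-stratified test is Z = Σ(O−E)/√ΣV over all 38. The stratified test computes both sums within each stratum and then adds them. A stratum with one person, or with people from one arm only, has n1/n equal to 0 or 1, so it adds nothing to either sum.

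**Plan's own figure first.** SAP 3.2.1 states 88% power at RD -35%. The un-stratified exact test, 19 per arm, on the scheduled visits, gives 88.5 to 89.7% across runs, which agrees within 2 points. The protocol attaches 88% to RD -30%. On the scheduled visits that effect gives 78.5%, which is why the RD -30% rows below start near 79%.

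**Larger early stratum** (asymptotic tests, same simulated trials, 200,000 per cell, un-stratified v stratified):

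| Early of 38 | Shift | Type I error | Power, RD -30% | Power, RD -35% |
|---|---|---|---|---|
| 6 | 0 | 0.102 v 0.103 | 79.4 v 78.7% | 89.1 v 88.6% |
| 6 | 1 | 0.096 v 0.101 | 79.7 v 80.1% | 89.1 v 89.4% |
| 10 | 1 | 0.094 v 0.103 | 80.1 v 81.1% | 89.5 v 90.1% |
| 4 | 2 | 0.084 v 0.102 | 79.5 v 81.4% | 88.8 v 90.1% |
| 6 | 2 | 0.083 v 0.103 | 79.6 v 82.5% | 88.7 v 90.8% |
| 10 | 2 | 0.072 v 0.102 | 81.2 v 85.1% | 89.5 v 92.2% |

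At shift 2 and RD -30%, the loss from ignoring the strata is 81.4 − 79.5 = 1.9, 82.5 − 79.6 = 2.9 and 85.1 − 81.2 = 3.9 points. At RD -35% it is 1.3, 2.1 and 2.7 points.

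**Very small early stratum.**
- None early: the two tests are the same (89.1% at RD -35%).
- Asymptotic, RD -35%, no shift: 89.1 v 88.4% (1 early) and 89.2 v 88.5% (2 early). With 2 early and shift 2: 88.5 v 88.8%.
- Exact tests, 8,000 trials: 78.5 v 77.2% (1 early, RD -30%; difference 1.3, SE 0.25) and 88.6 v 87.5% (2 early, RD -35%; difference 1.1, SE 0.20).
- Un-stratified type I error with 1 or 2 early and shift 0 to 1: 0.101 to 0.104, so not conservative.

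**Chance imbalance.** Two early participants can fall in the same arm through an incomplete block. At shift 2 the un-stratified error is then 0.111, above nominal. Its power at RD -30% is 69.1% if both are on active drug and 87.3% if both are on placebo. The stratified test gives 77.6% either way.

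**The case against.** The strongest case for the SAP is that the change is open, explained and sensible in the situation described. Section 11 declares it, SAP section 1 says that the SAP supersedes the protocol's statistics, and the protocol itself records the shortage. With one or two early participants a stratified test discards them or nearly so, and the un-stratified test is then slightly the more powerful. That stands. It rules out two stronger readings that a reader might draw: that dropping the strata can only lose power and make the test conservative, and that restoring them is free.

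It is also fair that the prognostic strength is assumed. The protocol's background section (2.1) places the highest viral loads in the first week of illness, but both strata lie within that week, so it gives no early-late contrast. At a shift of 1 the loss is about 1 point or less for 6 to 10 early participants. An early stratum much above 10 of 38 would sit badly with a reported shortage.

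Two further inferences are not supported. The stated 88% power was not shown to depend on stratification: the power sentence names an un-stratified test, and the curves assume treatment starting 72 to 96 hours after onset, which is inside the late stratum. And although protocol section 10.9 and SAP section 4.1 allow sponsor personnel to see unblinded virology data, nothing in the documents links that access to the change of test.

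What the objection does not supply is the early-stratum count, on which the SAP's justification rests.

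**Conclusion.** The point holds as a departure from analysing Part 1 as it was randomized. It is declared in the SAP but not supported there by a count. It is not a hidden contradiction.

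Its size is conditional. If 4 to 10 of 38 evaluable participants are early and onset time is strongly prognostic (logit shift 2), the un-stratified test runs at about 0.07 to 0.08 instead of 0.10 and loses about 2 to 4 points of power at RD -30%. With 1 or 2 early participants the tests are nearly equivalent, and stratifying costs about 1 point (1.3 at most in the exact runs). With none there is no difference. Across all these cases the stratified test stayed close to its nominal 10% level, and it is not moved by a chance imbalance in a tiny stratum.

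The balance therefore favours the protocol's test, modestly. Early-stratum size, prognostic strength and block size are all assumptions.

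**What to change.** In SAP section 11, and in sections 2.3 and 3.2.1 for consistency, restore the protocol's exact log-rank test stratified by early or late onset as the Part 1 primary test. Name the un-stratified exact test as a sensitivity analysis. Add early and late counts by arm to the Part 1 disposition or baseline tables, so that a reader can see which of the situations above applies.

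The cost is a few lines of SAP text, one stratification term in the program and one extra table row. The statistical downside is up to about 1 point of power if the early stratum turns out to be nearly empty. If the un-stratified test is nevertheless kept as primary, the SAP should state the early count that justifies it and specify the stratified test as the sensitivity analysis.
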